7 INVESTIGATIONAL PRODUCT HANDLING

7.1 Investigational Product Receipt

At study initiation and as needed thereafter, deucravacitinib and Enstilar will be shipped to a responsible person at the investigator's institution, who will check the amount and condition of the drug, and maintain a record of this information.

7.2 Investigational Product Storage

Investigational product will be stored per the storage conditions identified on drug label. At the study site, all IP will be stored in a locked, safe area to prevent unauthorized access.

Records of the actual storage conditions during the period of the study will be maintained.

8 RECORD RETENTION

The investigator must retain these documents according to local laws or requirements. Essential documents include, but are not limited to, the following:

- Signed informed consent documents for all subjects;
- Subject identification code list, screening log (if applicable), and enrollment log;
- Record of all communications between the Investigator and the IRB/EC;
 Composition of the IRB/EC;
- Record of all communications between the Investigator and Bristol Myers Squibb.
- List of Sub-investigators and other appropriately qualified persons to whom the Investigator has delegated significant study-related duties, together with their roles in the study, curriculum vitae, and their signatures;
- Copies of CRFs (if paper) and of documentation of corrections for all subjects;
- IP accountability records;
- All other source documents (subject records, hospital records, laboratory records, etc);

 All other documents as listed in Section 8 of the ICH consolidated guideline on GCP (Essential Documents for the Conduct of a Clinical Trial).

The Investigator must notify Bristol Myers Squibb if he/she wishes to assign the essential documents to someone else, remove them to another location or is unable to retain them for a specified period. The Investigator must obtain approval in writing from Bristol Myers Squibb prior to destruction of any records. If the Investigator is unable to meet this obligation, the Investigator must ask Bristol Myers Squibb for permission to make alternative arrangements. Details of these arrangements should be documented. All study documents should be made available if required by relevant health authorities. Investigator/Institution should take measures to prevent accidental or premature destruction of these documents.

8.1 Study Monitoring

The investigator will self-monitor all study records for accuracy, completeness, and compliance with the protocol and GCPs and federal regulations. All study records will be made available to Bristol Myers Squibb representatives upon request. Study site facilities and study records will be made available to regulatory authorities' inspectors if an inspection takes place. The investigator will notify Bristol Myers Squibb if this occurs.

8.2 Statistical Considerations

It is desired to enroll 30 patients. Since this is a pilot study with no formal hypothesis testing, statistical power/sample size is not formally presented in this protocol.

The study will analyze data based on the non-responder imputation (NRI) method. This will be performed for each arm of the study (PASI 75 responders at week 8 and PASI 25-74 responders at week 8. Subjects who do not complete week 12 assessments will be classified as non-responders

Analysis will be performed by the Investigator on proportion of subjects achieving Psoriasis Area Severity Index (PASI) 75 response at week 12

The investigator will also analyze PASI 25-74 at week 8, PASI, PGA, BSA, PGAxBSA and DLQI improvement at week 8, BSA, PGA and BSA x PGA and DLQI improvement at week 12. PASI, BSA, PGA, BSA x PGA and DLQI at weeks 16, 20 and 24. This analysis will be done separately for both cohorts (PASI 75 responders at week 8 and PASI25-74 responders at week 8) using summary statistics. The Investigator will also analyze SAE's by cohort.

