Main Exclusion Criteria	Subjects who meet any of the following criteria will be excluded from participation in this study: 1. Other than psoriasis, any clinically significant (as determined by the investigator) cardiac, endocrinologic, pulmonary, neurologic, psychiatric, hepatic, renal, hematologic, immunologic disease, or other major disease that is uncontrolled. 2. Forms of psoriasis other than chronic plaque-type (e.g., Pustular erythrodermic and/or guttate psoriasis) or drug induced psoriasis 3. Use of oral systemic medications or PUVA phototherapy for the treatment of psoriasis within 4 weeks (includes, but not limited to, oral corticosteroids, methotrexate, acitretin and cyclosporine). 4. Prior use of biologics within the following periods: • Etanercept – 4 weeks • Adalimumab or certolizumab pegol – 8 weeks • IL-17 antagonists – 16 weeks • Ustekinumab or IL-23 pathway inhibitors – 24 weeks • Other biologics - 5 half-lives 5. Patient used topical therapies or UVB phototherapy to treat psoriasis within 2 weeks of the Baseline Visit (includes, but not limited to, topical corticosteroids, vitamin D analogs, or retinoids).

Study Drug Dosage and Administration	All subjects will receive Deucravacitinib 6mg daily at week 0 (baseline) through week 8. At week 8, patients who achieved between PASI 25-74 response will receive 4 weeks of Enstilar (calcipotriene and betamethasone dipropionate) Foam, 0.005%/0.064% once daily in addition to continuing Deucravacitinib 6mg daily. At week 12 (after 4 consecutive weeks of Enstilar therapy), Enstilar will be discontinued and patients will continue Deucravacitinib 6mg daily as monotherapy through week 24. Patients who achieve ≥PASI 75 at week 8 will remain enrolled on Deucravacitinib 6mg QD monotherapy through week 24.
Study Endpoints	Primary Endpoint: Proportion of subjects achieving PASI 75 at week 12 for patients in the Deucravacitinib + Enstilar combination arm. Secondary Endpoints: Proportion of subjects achieving PASI 25-74 at week 8. PASI, PGA, BSA, PGAxBSA and DLQI improvement at weeks 8, 12, 16, 20, 24. PASI 75 at weeks 16 and 24 Serious Adverse Events (SAE's)
Study Duration	28 weeks

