5.5.2.3 Deucravacitinib Dosage Adjustments

If an SAE or an adverse event that is thought to be related to deucravacitinib and is not alleviated by symptomatic intervention, deucravacitinib will be discontinued. Subjects who permanently discontinue deucravacitinib therapy under this protocol should receive standard care of psoriasis treatment as prescribed by their physician.

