5.5.4 Permitted Concomitant Therapy

The use of steroid-free topical emollients is allowed during the study. Appropriate interventions (e.g., prescribed medications) may be performed as the investigator deems necessary to treat concomitant illnesses and/or safeguard the subjects' wellbeing. No investigational product or device may be used during the study.

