5.6.12 Early Discontinuation Procedures

Subjects will be prematurely discontinued from the study under the following conditions:

- 1. Subject does not reach PASI 25 or greater at week 8
- 2. Subject requests to withdraw from the study.
- 3. Subject is noncompliant with protocol schedule, restrictions, and/or requirements as deemed per investigator.
- 4. Subject experiences an adverse event that makes it difficult or intolerable for the subject to continue treatment, or increases risk to the subject, or interferes with the investigator's ability to clinically evaluate the progress of the subject's treatment.
- Subject begins an unapproved concomitant therapy for psoriasis or another medical condition that may increase risk to the subject if continuing study treatment.
- 6. Subject cannot be reached / lost to follow-up.
- 7. The study investigator suspends or terminates the study.
- 8. Other unanticipated reason.

Any subject who prematurely discontinues the study should complete the week 24 (End of Study) assessments and subjects should be encouraged return 4 weeks later for the safety follow up visit.

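### Section 8.2 ties week-12 non-response only to not completing the visit, so a PASI 75 reached after stopping deucravacitinib or on other psoriasis-active treatment can, by a few routes, count for the combination

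*Combined protocol and SAP*

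**What the plan says.** The synopsis (Study Endpoints) gives the primary endpoint as "Proportion of subjects achieving PASI 75 at week 12 for patients in the Deucravacitinib + Enstilar combination arm". That arm consists of the subjects with a PASI 25-74 response at week 8.

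Section 8.2 states: "The study will analyze data based on the non-responder imputation (NRI) method". It then defines one trigger: "Subjects who do not complete week 12 assessments will be classified as non-responders". It contains no outcome rule for stopping either drug or for using other treatment active in psoriasis.

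Four other sections bear on the point:

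- **5.6.12, item 5**, makes this a reason for leaving the study: "Subject begins an unapproved concomitant therapy for psoriasis or another medical condition that may increase risk to the subject if continuing study treatment". Item 4 covers adverse events that make treatment intolerable, raise risk or hamper clinical evaluation. After discontinuation: "Any subject who prematurely discontinues the study should complete the week 24 (End of Study) assessments".
- **5.5.2.3** stops deucravacitinib for certain adverse events and adds: "Subjects who permanently discontinue deucravacitinib therapy under this protocol should receive standard care of psoriasis treatment as prescribed by their physician". It mentions neither study withdrawal nor outcome status.
- **5.5.3.4** stops Enstilar for similar reasons, also without stating withdrawal or outcome status.
- **5.5.4** allows other medication: "Appropriate interventions (e.g., prescribed medications) may be performed as the investigator deems necessary to treat concomitant illnesses".

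The Schedule of Events (8.3) has no visit between weeks 8 and 12. PASI, BSA, PGA and DLQI appear in both the week-12 and week-24 columns.

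**The concern.** Non-responder imputation is often meant to do two jobs: to fail subjects with missing data, and to fail subjects whose observed value no longer reflects the study treatment. Section 8.2 writes down only the first. A subject who has changed or stopped treatment but has a week-12 PASI is therefore analysed as observed.

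The primary result is a single proportion in a subgroup of 30 subjects, with no concurrent control, so a few such subjects would be visible in it. The study is open-label (5.6), self-monitored (8.1) and analysed by the investigator (8.2). Without a written rule, these cases would be decided by someone who already knows the response.

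**Working it through.** The plan gives no power, alpha or expected rate, so there is no figure to reproduce. The check sets the sections side by side and then sizes the effect of one subject.

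**Step 1. Cases the plan already handles.** A subject who starts unapproved psoriasis therapy, or has an intolerable adverse event, and leaves before week 12 is discontinued under 5.6.12. That subject does the End of Study assessments on leaving. The week-12 assessments are not completed, so the 8.2 rule gives a non-responder.

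**Step 2. Cases left open.**

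| Route | Section that applies | What is not stated |
|---|---|---|
| (a) Switch between weeks 8 and 12, first found at the week-12 visit | 5.6.12 item 5; schedule 8.3 | Whether a PASI taken that day, possibly as an End of Study assessment, is the week-12 value |
| (b) Deucravacitinib stopped, standard psoriasis care started, subject attends week 12 | 5.5.2.3 | Whether the subject leaves the study, and how the outcome is counted |
| (c) Prescribed medication for another illness that also acts on psoriasis | 5.5.4 | How the outcome is counted |

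For route (a), the week-12 and week-24 columns of the schedule differ only in deucravacitinib dispensing. The same instruments would be completed under either label, so the label alone decides whether the 8.2 rule applies. For route (c), exclusion criterion 10 names oral corticosteroids among the psoriasis treatments needing a 4-week washout before entry. No matching analysis rule protects the week-12 PASI.

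A related case is early Enstilar stop under 5.5.3.4. The subject can remain in the study, attend week 12 and count in the combination arm without having completed the 4 weeks of Enstilar.

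**Step 3. Size per subject.** Inputs: 30 enrolled (8.2); combination-arm size m not stated, so assumed. If one subject with an observed PASI 75 is counted as a success when a composite rule would count a failure, the proportion is higher by 1/m:

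- m = 10: 1/10 = 10.0 percentage points
- m = 15: 1/15 = 6.7 points
- m = 20: 1/20 = 5.0 points
- m = 30 (every enrolled subject in the arm): 1/30 = 3.3 points, the smallest possible shift

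**Step 4. Illustration**, with an assumed 9 of 15 responders and exact (Clopper-Pearson) 95% intervals:

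| Subjects reclassified | Responders | Proportion | 95% interval |
|---|---|---|---|
| 0 | 9/15 | 60.0% | 32.3 to 83.7 |
| 1 | 8/15 | 53.3% | 26.6 to 78.7 |
| 2 | 7/15 | 46.7% | 21.3 to 73.4 |

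One or two subjects move the estimate noticeably, though by less than the sampling uncertainty in an arm of this size.

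**The case against.** The best reply is that 5.6.12 already does most of this work. Switchers are removed under item 5, and many who stop deucravacitinib for an adverse event fall under item 4. If they leave before week 12 they are non-responders without further wording. A subject withdrawn at week 10 or 11 does the End of Study assessments then; returning at week 12 for efficacy is not the path 5.6.12 sets out. Items 3 and 8, and the part of item 4 on hampered evaluation, give the investigator further discretion, including for some subjects treated for another illness. This stands, and it confines the concern to the routes in the working.

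A reader might infer that an End of Study PASI taken around week 12 automatically becomes the week-12 value. No section says so. Sharing instruments does not make the two visits the same, so this is an ambiguity and not a demonstrated error. Nor do the documents support saying that switches would usually come to light only at week 12. They show that no visit is scheduled in between, but a subject may report a change earlier.

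A reader might also infer that the primary estimate is biased upward in general. That goes too far. A subject matters only if the observed PASI response reaches 75, and stopping deucravacitinib without an effective replacement could plausibly lower response. What holds is narrower: compared with a rule that fails these subjects, the present wording can only leave successes standing.

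Finally, counting stoppers and switchers as failures is a choice of estimand, and the study is a descriptive pilot without hypothesis testing. Type I error and power are not at issue. The choice still needs to be written down before the responses are known.

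**Conclusion.** The concern holds in limited form. Completing the week-12 assessments is the only written criterion separating observed from imputed outcomes, and three routes remain by which a PASI 75 reached after stopping deucravacitinib, or on other psoriasis-active treatment, could be credited to the combination. Each such subject adds 1/m to the primary proportion: 10.0, 6.7 or 5.0 points for assumed arms of 10, 15 or 20, and 3.3 points at the least.

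These figures rest on assumed arm sizes and on the subject's PASI response reaching 75. The documents give no basis for estimating how many subjects would be affected, and the number may be small or zero. The shifts of 5 to 10 points are therefore effects per case, not an expected bias. The point affects the estimate and its interpretation, and is worth settling because the remedy is cheap.

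**What to change.** Add to section 8.2, as an analysis rule only:

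> Subjects who, before the week-12 PASI, permanently stopped deucravacitinib, started a psoriasis therapy other than study drug and permitted emollients, or met a 5.6.12 discontinuation condition are non-responders at week 12 whether or not a PASI was obtained. An End of Study PASI from such a subject does not count as the week-12 value.

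List these subjects with their observed PASI, so that readers can see what the rule changed.

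Two groups are better handled outside the main rule. Subjects given a psoriasis-active systemic drug for another illness should not all be failed automatically, since dose, duration and timing differ. Subjects who stopped Enstilar early (5.5.3.4) may still have had part of the combination. List both groups and show a sensitivity analysis counting them as non-responders.

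The rule needs dates. The schedule provides for concomitant-medication and IP accountability reviews, and 5.5.2.2 records deucravacitinib dispensed, returned and missed, but start and stop dates are only implied. State that they are to be recorded at those reviews.

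The cost is a short addition to 8.2, one listing, one sensitivity analysis and explicit date fields. No treatment, visit or procedure changes. The reported PASI 75 rate may be slightly lower.

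### Does the plan leave PASI 75 at weeks 16 and 24 without an analysis or a rule for subjects who leave early?

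*Combined protocol and SAP*

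**What the plan says.** The Study Endpoints row of the synopsis gives PASI 75 at week 12 in the combination arm as primary. Its secondary endpoints include "PASI 75 at weeks 16 and 24" and "PASI, PGA, BSA, PGAxBSA and DLQI improvement at weeks 8, 12, 16, 20, 24".

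Section 8.2 (Statistical Considerations) is short. It starts from a target, "It is desired to enroll 30 patients", and describes a pilot without formal hypothesis testing. On missing data it says "The study will analyze data based on the non-responder imputation (NRI) method", applied to each of the two cohorts formed at week 8, and then "Subjects who do not complete week 12 assessments will be classified as non-responders". On response it says "Analysis will be performed by the Investigator on proportion of subjects achieving Psoriasis Area Severity Index (PASI) 75 response at week 12". For the other outcomes it lists, by cohort and with summary statistics, all five measures at week 8, then "BSA, PGA and BSA x PGA and DLQI improvement at week 12", then "PASI, BSA, PGA, BSA x PGA and DLQI at weeks 16, 20 and 24".

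Section 5.6.12 has anyone who leaves prematurely undergo the procedures of the week-24 visit. Section 8.3 (Schedule of Events) has PASI at weeks 8, 12, 16, 20 and 24. Section 8.2.1 allows a separate statistical plan, but only for optional exploratory work.

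**The concern.** Read literally, the endpoint list and the analysis list differ. Section 8.2 does not name PASI 75 at week 16 or week 24, and its week-12 improvement list leaves out PASI. The only spelled-out non-responder rule depends on completing week 12, so a subject who completes week 12 and leaves before week 24 falls outside its wording.

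The exit visit adds to this. Such a leaver has a PASI collected under the week-24 procedures and is therefore not plainly missing. If that score were used as a week-24 value, it could stand for an earlier time. It could also reflect another treatment, because starting an unapproved psoriasis therapy is one of the listed reasons for leaving.

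What is at stake is the responder measure of durability. Enstilar stops at week 12, and PASI 75 at weeks 16 and 24 shows whether response lasts on deucravacitinib alone. NRI at each visit, observed cases and exit-as-week-24 could give three different rates.

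**Working it through.** The plan gives no power, derived sample size or expected rate here, so there is no figure to reproduce. The check is mainly a comparison of texts.

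**1. Are the later PASI 75 results called for?** Yes. The synopsis names them and the Schedule of Events collects PASI at both visits. Section 8.2 includes PASI in "PASI, BSA, PGA, BSA x PGA and DLQI at weeks 16, 20 and 24", by cohort. That clause drops the word improvement, which section 8.2 uses for weeks 8 and 12, so it can include the proportion reaching PASI 75. The mention of week 20 does not count against this reading: the clause covers five measures, and the synopsis lists all five at week 20.

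**2. PASI improvement at week 12.** The synopsis lists it and the schedule collects PASI at that visit. Section 8.2 names PASI 75 at week 12 in the sentence just before the list that omits PASI. This is a clerical slip; the data and the commitment both exist.

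**3. Does NRI reach weeks 16 and 24?** The general sentence, "The study will analyze data based on the non-responder imputation (NRI) method", names no visit. It covers both cohorts, including the subjects already at PASI 75 at week 8, who are outside the primary endpoint. NRI is therefore not confined to the primary analysis. The week-12 sentence spells the rule out for the primary visit and does not switch it off later.

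**4. Is an exit visit a week-24 value?** Section 5.6.12 says which procedures to perform. It does not say that the result is analysed at week 24. The same instruction covers subjects who leave at week 8 for not reaching PASI 25. Their scores could not sensibly be week-24 data, and they belong to neither cohort. Relabelling exit scores would be a misreading that no section directs.

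**5. Score outcomes.** NRI is a method for responder outcomes and supplies no value for a score. Section 8.2 provides summary statistics for scores, which is ordinary in a descriptive pilot.

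**6. How far could the readings diverge?** The documents give neither cohort sizes nor numbers of leavers, so every input here is an assumption. Let m be the cohort size at week 8, e the leavers after week 12, r the stayers at PASI 75 at week 24, and k the leavers at PASI 75 at exit.

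- NRI at each visit: r/m
- Observed cases: r/(m − e)
- Exit counted as week 24: (r + k)/m, which exceeds NRI by k/m

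With m = 15, e = 2, r = 6:

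| Reading | Formula | Rate |
|---|---|---|
| NRI | 6/15 | 40.0% |
| Observed cases | 6/13 | 46.2% |
| Exit as week 24, k = 0 | 6/15 | 40.0% |
| Exit as week 24, k = 1 | 7/15 | 46.7% |
| Exit as week 24, k = 2 | 8/15 | 53.3% |

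The exact (Clopper-Pearson) 95% interval around 6/15 runs from 16% to 68% and contains every value in the table.

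If all leavers are at PASI 75 at exit (k = e), the gap between NRI and exit-as-week-24 is e/m. Over m = 10 to 25 and e = 1 to 3 it runs from 1/25 = 4 points to 3/10 = 30 points. It is zero if nobody leaves after week 12 or if no leaver is at PASI 75 at exit.

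**The case for a change.** The best case for a change is that the study is open-label and the investigator does the analysis, so a rule fixed before the data are seen has value even in a pilot. Section 8.2 writes PASI 75 when it means a response proportion, so a bare PASI at weeks 16, 20 and 24 may mean only the score. The general NRI sentence does not fully settle the exit question either, because NRI fills missing values and a leaver with an exit PASI has a recorded one. The later visits also matter scientifically: the rationale in section 3.2 cites PASI 75 maintained on monotherapy in a similar apremilast trial. A few sentences would remove the doubt at little cost.

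Part of this stands. The two lists are not worded alike, and no sentence assigns exit assessments to an analysis visit. Writing the convention down would be tidy. But no stated rule yields a wrong result. The larger gaps arise only if several leavers in a small cohort are at PASI 75 at exit and an analyst also relabels their visits against the plain sense of section 5.6.12. The added sentences would mostly record what a competent analyst would do anyway.

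**Conclusion.** No change follows. This is missing detail that analysts fill sensibly, together with one clerical omission (PASI improvement at week 12). The synopsis, the Schedule of Events and section 8.2 together support reporting PASI 75 at weeks 16 and 24 by week-8 cohort, with leavers counted as non-responders and exit scores kept at the study week when they were taken.

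The size of any effect cannot be known from the documents and may be zero; the figures above rest on assumed cohort sizes, leavers and responders. The consequence is limited to secondary, descriptive results in a pilot with a target of 30 subjects and no hypothesis test. The primary endpoint is unaffected, since a subject who does not complete week 12 is already a non-responder.

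The conclusion assumes that NRI is applied at each visit and that exit visits are not relabelled as week 24. A report that did otherwise should say so.

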3.2 Rationale for Treating Plaque Psoriasis with Deucravacitinib + Enstilar

Deucravacitinib is an investigational TYK2 inhibitor that has been tested for the treatment of moderate-to-severe psoriasis. Combination regimens that utilize a systemic agent with light therapy and/or a topical agent are becoming the standard of care in the United States³ and Europe⁴, confirming the observation of Lebwohl et al⁵ in 2004, that the use of two or more therapies to treat patients with moderate to severe psoriasis seems to be the rule rather than the exception. Topical steroids play an in important role in the long-term management of psoriasis and data from the COBRA trial suggests that super potent topical corticosteroids are appropriate and well tolerated for use when added to existing therapeutic regimens i.e. phototherapy, systemic and biologic therapy.⁶ In a similarly designed clinical trial using apremilast with Enstilar add- on therapy it was shown that most week-8 partial apremilast responders achieved PASI 75 at week 12 with combination C/BD topical therapy, and maintained PASI 75 through week 16 with apremilast monotherapy.⁷ This study is being conducted to determine if adding topical Enstilar to deucravacitinib therapy can help patients who received a partial response at week 8 reach PASI 75 by week 12.

4.STUDY OBJECTIVES

The primary objective of this study is to explore the effectiveness of combining deucravacitinib and Enstilar. Secondary objectives will explore the safety and impact on quality of life for subjects receiving deucravacitinib in combination with Enstilar.

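### Does Section 8.2 need to name the combination cohort and plan a confidence interval for the week 12 PASI 75 proportion?

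*Combined protocol and SAP*

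**What the plan says.** The synopsis (Study Endpoints) defines the primary endpoint as "Proportion of subjects achieving PASI 75 at week 12 for patients in the Deucravacitinib + Enstilar combination arm". That arm consists of the subjects whose week 8 response lies in the PASI 25-74 band (Section 5.1).

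On enrolment, Section 8.2 says "It is desired to enroll 30 patients". It then explains that, as a pilot without formal testing, the study presents no power or sample size calculation. On missing data it says "The study will analyze data based on the non-responder imputation (NRI) method", adds that this is done for each arm, names the two week 8 cohorts (PASI 75 responders and PASI 25-74 responders), and continues: "Subjects who do not complete week 12 assessments will be classified as non-responders". The planning sentence for the main result follows: "Analysis will be performed by the Investigator on proportion of subjects achieving Psoriasis Area Severity Index (PASI) 75 response at week 12". The further endpoints are then listed, with separate descriptive summaries for the two cohorts.

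No confidence level, interval method or other precision measure appears. Section 8.2.1 allows a separate statistical plan, but only for optional exploratory work.

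**The concern.** There are two apparent gaps.

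First, the planning sentence speaks of subjects in general, while the synopsis restricts the endpoint to one cohort. Read in isolation, it would allow several denominators, and these can give quite different percentages.

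Second, with no hypothesis test the estimated rate is the whole primary result, and it comes from an unknown fraction of 30 people. The rationale in Section 3.2 reports that "most week-8 partial apremilast responders achieved PASI 75 at week 12 with combination C/BD topical therapy". A bare percentage near two thirds could be read as repeating that finding when the data are also compatible with a rate below one half. Disclaiming power does not answer this, because an interval belongs to estimation and not to testing.

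A side issue is that the synopsis lists "PASI 75 at weeks 16 and 24" as a secondary endpoint, whereas Section 8.2 lists "PASI, BSA, PGA, BSA x PGA and DLQI at weeks 16, 20 and 24" without repeating the responder definition.

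**Working it through.** **No stated figure to reproduce.** The documents give no alpha, power, assumed response rate, cohort size or precision target. The only number is the enrolment aim of 30.

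**Step 1: is the denominator open?** Take an assumed split of the 30: 15 in the combination cohort (9 with PASI 75 at week 12), 10 week 8 PASI 75 responders (9 still at PASI 75 at week 12) and 5 discontinued at week 8. The possible readings are:

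| Reading | Proportion |
|---|---|
| Combination cohort only | 9/15 = 60% |
| Both cohorts pooled | (9 + 9)/(15 + 10) = 18/25 = 72% |
| All enrolled, discontinued counted as failures | 18/30 = 60% |
| Combination responders over all enrolled | 9/30 = 30% |

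The choice could matter, so the text has to decide it, and it does. The synopsis restricts the endpoint to the combination arm, which excludes the second and third readings. By-arm imputation keeps the arm as the unit of analysis, which excludes the fourth. Subjects without week 12 assessments stay in the denominator as failures. Only the first reading fits all three statements.

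**Step 2: how wide would the interval be?** Assume that one third to two thirds of the 30 enter the combination cohort. The 2.5th and 97.5th percentiles of a Binomial(30, p) count are 5 and 15 for p = 1/3, 10 and 20 for p = 1/2, and 15 and 25 for p = 2/3. Together they span 5 to 25 subjects.

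For x responders out of n, with p = x/n and z = 1.96:

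- Exact (Clopper-Pearson): the lower limit is the 2.5th percentile of Beta(x, n − x + 1); the upper limit is the 97.5th percentile of Beta(x + 1, n − x).
- Wilson: [p + z²/(2n) ± z·√(p(1 − p)/n + z²/(4n²))] / (1 + z²/n).

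Wilson for 13/20: the centre is (0.65 + 0.0960)/1.1921 = 0.626 and the half-width is 1.96 × √(0.011375 + 0.002401)/1.1921 = 0.193, which gives 43.3% to 81.9%.

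| x/n | Rate | Exact 95% | Width (points) | Wilson 95% |
|---|---|---|---|---|
| 7/10 | 70.0% | 34.8–93.3 | 58.6 | 39.7–89.2 |
| 10/15 | 66.7% | 38.4–88.2 | 49.8 | 41.7–84.8 |
| 13/20 | 65.0% | 40.8–84.6 | 43.8 | 43.3–81.9 |
| 17/25 | 68.0% | 46.5–85.1 | 38.6 | 48.4–82.8 |
| 17/24 | 70.8% | 48.9–87.4 | 38.5 | 50.8–85.1 |
| 18/25 | 72.0% | 50.6–87.9 | 37.3 | 52.4–85.7 |
| 23/25 | 92.0% | 74.0–99.0 | 25.0 | not needed |

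**Step 3: how firm is the 50% argument?** For n from 5 to 25 there are 17 counts with a rate between 65% and 70%. All have a lower limit below 50%; the highest is 47.1% (exact) and 49.1% (Wilson), both at 16/23. The pattern ends just above the band: 17/24 clears 50% by Wilson, and 18/25 clears it by both methods. The 50% line is also not in the plan. The word in Section 3.2 describes another study's result and sets no criterion for this one.

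**Step 4: what would change in the result?** The proportion x/n is the same whether or not an interval is printed beside it. No decision in the plan depends on a limit.

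**The case for a change.** The strongest case for a change is that the primary output has no planned measure of uncertainty, that the investigator performs the analysis of an open-label study, and that the interval method should be fixed before the data are seen, because the exact and Wilson limits can fall on opposite sides of a reference value (17/24 is an example). The remedy would cost two or three sentences.

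Much of this is true as description. No interval is planned, the intervals would be wide, and stating one in advance is good practice. It does not show that the plan goes wrong:

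- The method matters only if something depends on a limit, and nothing here does. Even against 50%, the smallest count whose lower limit exceeds it is the same by both methods at n = 10, 15, 20 and 25 (9, 12, 15 and 18).
- The plan does not exclude intervals, and does not say that a percentage will be given without its count.
- Part of the suggested wording, counting subjects without week 12 assessments as failures, is already in Section 8.2.
- The point about weeks 16 and 24 is a separate matter of wording. The opening imputation sentence is general and can be read to cover those visits, and PASI 75 there follows from the PASI scores that are collected.

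**Conclusion.** No change follows. The cohort part is a loose sentence that the synopsis and the neighbouring text of Section 8.2 resolve: the primary result is the number with PASI 75 at week 12 over all subjects in the week 8 PASI 25-74 cohort, with those lacking week 12 assessments counted as failures. The interval part is a reporting detail that a competent analyst would supply and any reader can calculate.

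The imprecision itself is real: about 44 to 59 points of exact 95% width for an assumed cohort of 10 to 20 and a rate near two thirds, falling to 25 points at 23/25. It comes from the small pilot cohort, and planning an interval would display it without reducing it. These widths rest on assumed cohort sizes and rates, and 50% serves only as an illustrative reference. A 95% exact interval beside the count would be a welcome addition to the report. Without it the plan still gives a sound estimate and no wrong result.
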